#### 4.3.5. Concomitant medications

All patients participating in the trial should receive treatment according to evidence-based guidelines. Concomitant medications are recorded throughout the study.

#### 4.3.6. Safety

- serum calcium, phosphorus, to detect for vitamin D intoxication (every 3 months)
- measurement of total WBC and differential (every 6 months) and a record of infection rate (every 3 months) to check for immunosuppressive effects

## Adverse clinical events

All serious events will be reported to the Leuven coordinating Centre. See also section 6.4.

### **4.3.7. Data Safety Monitoring Board (DSMB)**

All safety parameters and adverse events will be reviewed by a DSMB. The DSMB is unblinded and composed of medical experts not involved in the study: a dermatologist, oncologist and statistician. They will assess the safety of patients based on the safety parameters and adverse events. In particular, at regular intervals an unblinded interim analysis will be performed to assess the difference between the intervention arms and to exclude an increase in relapse rate in the vitamin D supplemented arm. No early stopping for efficacy will be allowed. Details of the DSMB responsibilities will be documented in a charter.

#### **4.3.8. Study duration for study patients**

Each enrolled patient will remain in the study throughout the entire study duration, with a maximum study follow-up of 3.5 years for each patient. A study patient's participation may be terminated early because of relapse/progression which is the main study end point or due to a reasonable cause, such as the investigator's medical decision. At any time, the patient has the right to withdraw consent without a negative impact on her/his medical treatment.

#### **4.3.9. Duration of the whole study**

Our power calculations are based on a patient enrolment rate of 500 melanoma patients during a recruitment phase of three years maximum. Concerning the enrolment period: the first patient will be recruited as of fall 2012 and the last patient in fall 2023. In order to meet those targets, a multiple center study is necessary, via participation of other academic centers.

The DSMB may terminate the study earlier based on safety concerns at any time. The sponsor may also terminate the study early for reasonable cause. Competent authorities/ethics committees retain the right for premature termination of the study according to applicable regulations. The study may also be terminated early if the work performed is not compliant with Good Clinical Practice.

### **5. INVESTIGATIONAL MEDICINAL PRODUCT**

#### **5.1. D-Cure® (cholecalciferol)**

##### **5.1.1. General information**

- Name investigational product: D-Cure® (amp. cholecalciferol 100.000 U.I./ml)  
Content of 1 ml amp.: Cholecalciferol 100.000 U.I./ml -DL α-Tocopherol. acetas  
-  
Sorbitol. oleic. polyoxyaethylenat. - Aetherol. aurantii corticis dulcis - olie van  
olijfolie ad 1 ml
- Administration route: orally
- General properties: clear, (light) yellow oil

\* D-Cure® amp. 100.000 U.I/ml

Licence number: BE436073

Licence holder: Laboratoires SMB NV, [name]

Manufactured by SMB Technology S.A., [name]

- Quality control tests for + specifications:

Since D-Cure® is a licenced drug, all quality control tests are performed by Laboratoires SMB.

For more information about D-Cure®: see the scientific package leaflet in attachment.

- \* D-Cure® ampoules 100.000 U.I/ml are delivered in a blinded manner by Laboratoires SMB NV.

### 5.1.2. Labelling

- Local Pharmacy labels the D-Cure® ampoules
- Example of label

Protocol: ViDMestudy	Investigator: of local academic center
Vitamin D 100.000 IU vs placebo	
Pro ampoules	1ml
Lot: ..... Expiration date: .....	
Store at roomtemperature	
Exclusively for clinical research	

- 

### 5.1.3 Storage

D-Cure® (oral ampoules) will be stored at room temperature, below 25 °C. Temperature (minimum and maximum temperature) is recorded electronically every working day.

### 5.1.4 Transfer

After release by a responsible person, the IMP's can be transferred to the investigator, using a signed transfer document. IMP will not be transferred to another site.

### 5.1.5. Use, accountability and destruction

Pharmacists of the University Hospitals Leuven, who are independent from the clinical study team, will randomly assign participants by using a computer-generated randomization list and prepare the study medication. A diary will be given to the patient for dates when to take the medication (numbered syringes) on a monthly base, at a dose of 100 000 IU (1 ml of D-cure® suspension in ) or 1 ml of placebo (olive oil). Vitamin D and placebo are prepared by Laboratoires SMB NV in oral ampoules , identical in taste and appearance. Oral ampoules are numbered according the randomization schedule. At each visit 3 numbered ampoules are given to the patient, Patient will take empty ampoules back to the control visit (every 3 months). Number of ampoules and date the Vitamin D/placebo is taken are registered. Subsequently empty ampoules are destroyed

## 5.2. Olive oil

### 5.2.1. General information

Name investigational product: Olive oil

Olive oil will be used as matching placebo for vitamin D (cholecalciferol)

Composition: Tocopherol Acetate, sweet orange peel oil, Polyglyceryl oleate, olive oil refined ad 1ml

- Administration route: orally
- General properties: clear, (light) yellow oil
- Olive oil

- Quality control tests for + specifications:

Since Olive oil is manufactured by Laboratoires SMB and all quality control tests are performed by Laboratoires SMB.

Placebo ampoules are delivered in a blinded manner by Laboratoires SMB NV.

### 5.2.2. Labelling

Local pharmacy labels the placebo ampoules.

Example of label

Protocol: ViDMestudy      Investigator: of local academic center  
Vitamin D 100.000 IU vs placebo  
Pro ampoule      1ml  
Lot: ..... Expiration date: .....  
Store at roomtemperature  
Exclusively for clinical research

### 5.2.3. Storage

The -Olive oil (oral ampoules) will be stored at room temperature, below 25°C. Temperature (minimum and maximum temperature) is recorded electronically every working day.

### 5.2.4. Transfer

After release by a responsible person, the IMP's can be transferred to the principal investigator of each site, using a signed transfer document. IMP will not be transferred to another site.

### 5.2.5 Use, accountability and destruction

See active product

## 6. ADVERSE EVENTS AND CLINICAL EVENTS

### 6.1. Definitions

#### 6.1.1. Adverse event

An adverse event (AE) is defined as any untoward medical occurrence in a patient administered an investigational medicinal product and which does not necessarily have a causal relationship with this treatment.

### 6.1.2. Serious and non-serious adverse events

All AEs fall into either the category “non-serious” or “serious”. A serious adverse event (SAE) is any untoward medical occurrence that at any dose:

- Results in death
- Is life-threatening
- Requires inpatient hospitalisation or prolongation of existing hospitalisation
- Results in persistent or significant disability or incapacity
- Is a congenital anomaly or birth defect
- Is an important medical event

A non-serious adverse event is any untoward medical occurrence that does not fulfil any of the criteria listed above.

Adverse events with respect to abnormal assay results and precautionary safety procedures to be taken:

- Clinical significant hypercalcemia: defined as 2 independent measurements (2 different laboratories), above the reference value; action taken: end of study
- HypervitaminoseD: defined as 25(OH)D3 > 80 ng/ml; action taken: discontinue study drug and restart monthly treatment with study drug when 25(OH)D3 falls below 50 ng/ml on 3 monthly monitoring .
- Hypovitaminose D:
  - \* Serum 25(OH)D3 < 10 ng/ml at baseline; action taken: supplementation of extra vitamin (D-cure): 25000IU / month,
  - \* Serum 25(OH)D3 < 10 ng/ml at 6 months or later; action taken: end-of-study
  - \* Serum 25(OH)D3 > 10 ng/ml and < 20 ng/ml at baseline: supplementation of extra vitaminD (D-cure): 25000IU/month
  - \* Serum 25(OH)D3 > 10 ng/ml and < 20 ng/ml at 6 months or later: supplementation of extra vitaminD (D-cure): 25000IU/month
- Hypophosphatemia: < 1.5 mg/dl: further investigation
- Hyperphosphatemia: > 6mg/dl: further investigation

*Clarification of the difference in meaning between “severe” and “serious”*

Confidential

#

page 40 of 52

The term “severe” is often used to describe the intensity (severity) of a specific event (see next section below); the event itself, however, may be of relatively minor medical significance (such as severe headache). This is not the same as “serious”, which is based on the outcome or action criteria usually associated with events that pose a threat to life or functioning. Seriousness (not severity) serves as a guide for defining regulatory reporting obligations.

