## PROTOCOL SYNOPSIS

Title	The ViDMe Project "Vitamin D supplementation in cutaneous malignant melanoma outcome"
EudraCT No.	2012-002125-30
Phase	III
Sponsor	UZ Leuven
Coordinating Investigator	[name]
Study Objectives	To assess whether vitamin D supplementation, in the follow up period after diagnosis and surgery of the primary tumor, has a protective effect on relapse of cutaneous malignant melanoma and whether this protective effect correlates with vitamin D levels in serum and vitamin D receptor (VDR) immunoreactivity in the primary tumor.
Design	double-blind randomized placebo-controlled study
Treatment Groups	Group 1: optimal standard of care (control group) Group 2: high dose vitamin D3 supplementation added on top of optimal standard of care. Patients will be randomised to treatment or control group in a 1:1 ratio.

Study Flow and Assessments	
The study is divided into three parts:
 

• Screening phase: Patients are recruited at the Departments of Dermatology, Oncosurgery or Medical Oncology at the University Hospitals Leuven (Belgium), and other European academic sites. If all eligibility criteria are met, patients are then randomized to the treatment or control group. Randomisation is completed via IVRS. Patients are randomized as they come.

• Treatment phase: Vitamin D3 supplementation is given to the patients assigned to the treatment group and placebo to the control group in a double blind manner. Every participant is expected to take in the study drug orally once each month. Study duration is a maximum of 3.5 years or until relapse occurs.

• Follow-up phase: Every participant will be followed up every 3 months up to the final study visit. Endpoints will be reported as occurring throughout the follow up. Defined endpoints are adjudicated by an independent Clinical Endpoint Committee (CEC) blinded to the patient treatment allocation. This ensures a consistent and unbiased adjudication of events.

 
Study data are reviewed by a Data and Safety Monitoring Board (DSMB) that reviews key safety data on an ongoing basis.

-----------------------------------	--

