### **3.2. Justification of study design**

A previous study has demonstrated the association of higher 25-hydroxyvitamin D3 serum levels with lower Breslow thickness of the tumor at diagnosis (Newton-Bishop, 2009), suggesting a protective effect of higher vitamin D levels on disease progression of cutaneous malignant melanoma.

To further proof the protective effect of Vitamin D supplementation on melanoma disease progression, this study will give high dose vitamin D supplementation to the melanoma patients after surgery of the primary tumor ( which is the current best standard of care), in a placebo controlled and double blind way. The effect of high dose vitamin D supplementation in double blind placebo controlled way will be primarily tested on relapse free survival.

Patients will be randomly assigned in a 1:1 ratio to receive a monthly oral dose of 100 000 IU of vitamin D (1ml of D-Cure) or placebo (1 ml of olive oil). A block randomization method stratified on time of diagnosis (newly diagnosed, 0-6 months or 6-12 months before start of the study) will be used to overcome seasonal influences on baseline characteristics.

We will also assess the expression of the Vitamin D Receptor (VDR) expression in the primary tumor. A blood sample will be taken for DNA analysis (genetic variability in the vitamin D pathway). We will check 25(OH)D3 serum levels both at diagnosis, and every 6 months until the end of the study. If the level of 25(OH)D3 serum is above 80 ng/ml, study drug will be interrupted and during drug free interval the 25(OH)D3 serum levels will be checked every 3 months. When serum 25(OH)D3 falls below 50 ng/ml, study drug is restarted

The patient cohort will exist of 3 subgroups (patients diagnosed within 6 or 12 months before start of the study and newly diagnosed patients). Inclusion of previously diagnosed patients will allow us to assess whether delayed supplementation has a similar effect on the relapse free survival rate as immediate supplementation after surgery of the tumor.

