**Table 1: Schedule of assessments**

	Screening	Randomization = day 0	Every 3 months FU	Every 6 months FU	End of Study (fall 2023) or Progression/Relapse
Informed Consent	X				
Demographics	X				
Medical History	X				
Melanoma Risk Factors	X				
Sun exposure Behaviour	X				X
Physical Examination	X		x		X
Vitamin D levels		X		X	X
DNA analysis		x			
Safety Laboratory#	X		X	x	X
Concomitant Medications	X	X	X		X
Adverse Event / Endpoint Collection		X	X		X
24 hour urine calcium					X

+

#

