## 4.2. Patient screening and randomization

Patients are recruited upon presentation and recruitment is based on the stage of melanoma.

Stage IB-III patients will be enrolled from fall 2012 to fall 2023.

After staging and surgical treatment, and after obtaining written informed consent, patient will undergo screening at the investigational site to ensure that the patient meets all other in- and exclusion criteria. Written informed consent must be obtained from patients prior to any study specific procedure (for details see section 8.1). After consenting patients undergo the procedures listed for the screening visit. If the patient meets all in- and exclusion criteria, the patient will then be randomized using a specifically designed Interactive Voice Response system (IVRS) on an equal basis (1:1) to either vitamin D or placebo stratified on time of diagnosis (newly diagnosed, 0-6 months or 6-12 months before start of the study). The IVR system will supply a patient number that will be used as the key identifier for the entire study period. Patients in both arms will receive similar looking capsules, containing either 100 000 IE cholecalciferol or placebo oil. The randomization schedule will be kept under closure at the data management centre. All other study staff members, dermatologists, trial nurses, and patients will be blinded to the treatment allocation. The DSMB members may be unblinded to assess the safety of the patients. The study complies with the Helsinki declaration of medical research and needs approval by the hospital medical ethics committee. Written informed consent will be obtained prior to enrolment.

In these stage IB-III melanoma patients (500 patients), we will take a blood sample for serum analysis (25(OH)D3 levels) at the moment of diagnosis and, every 6 months until relapse or until the end of the study.

Every participant will also be asked to complete a questionnaire regarding melanoma risk factors, including amount and type of sun exposure and to undergo skin examination for the assessment of phototype, naevus phenotype and actinic damage. We will measure patient's height and weight, which will be used to estimate body mass index (BMI).

Our power calculations are based on a patient enrolment rate of 500 melanoma patients until the end of the study. In order to meet those targets, a multicentre study is necessary, via participation of other academic centers.

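### The end-of-study action for 25(OH)D3 below 10 ng/ml is undefined; read literally it ends relapse follow-up mostly in placebo patients, with a small effect that a cheap rewording removes

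*Combined protocol and SAP*

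**What the plan says.** Section 6.1.2 lists actions for abnormal laboratory results. Two of them end the study:

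- Low vitamin D: "Serum 25(OH)D3 < 10 ng/ml at 6 months or later; action taken: end-of-study".
- Confirmed hypercalcaemia, on two measurements: "2 different laboratories), above the reference value; action taken: end of study".

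For a high vitamin D level the same list acts on the drug only: "action taken: discontinue study drug and restart monthly treatment with study drug when 25(OH)D3 falls below 50 ng/ml". Section 3.2 agrees: "If the level of 25(OH)D3 serum is above 80 ng/ml, study drug will be interrupted".

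The general rules point to complete follow-up. The synopsis says "Every participant will be followed up every 3 months up to the final study visit", and section 4.3.8 says "Each enrolled patient will remain in the study throughout the entire study duration". Section 4.3.8 also lets participation end early for a reasonable cause, and section 6.3 stops collection of serious adverse events at premature termination.

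Section 7.2 analyses all randomised patients in their randomised arm. It states no censoring rule and leaves details to a statistical analysis plan that is not in the file. Section 7.1 assumes that nobody is lost to follow-up.

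**The concern.** Section 6.1.2 uses drug-only wording for one trigger and different wording for two others, so a site could reasonably take the latter to mean that the patient leaves the trial. Elsewhere the term can mark the close of assessments: the last column of Table 1 is headed "End of Study (fall 2023) or Progression/Relapse", and section 4.2 takes serum samples "every 6 months until relapse or until the end of the study". No section orders relapse visits after either trigger. Section 6.4.5 does order follow-up after a patient's study is ended, but for a pregnancy.

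If sites stop relapse visits, loss of outcome data depends on a marker measured after randomisation and changed by treatment. Sections 1.1 and 1.3 expect 100 000 IU monthly to raise levels from below 20 to about 50 ng/ml. A value below 10 ng/ml from month 6 would then occur mostly on placebo, or in active patients who do not take the drug. On the trial's own hypothesis, those patients may relapse more often. At stake is censoring that differs between arms and may be informative, in a trial that needs only about 51 events.

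**Working it through.** **Planned figure.** Section 7.1 claims 90% power for a hazard ratio (HR) of 0.40 with 500 patients. It gives neither alpha nor a control relapse rate, so the claim cannot be fully reproduced. Assuming two-sided 0.05 and 1:1 allocation, Schoenfeld's formula gives

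D = 4 × (1.960 + 1.282)² / (ln 0.40)² = 4 × 10.51 / 0.8396 = 50.1, so 51 events.

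Power at 51 events = Φ(|ln 0.40| × √(51/4) − 1.960) = Φ(3.272 − 1.960) = 0.905.

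With 250 per arm, 51 events imply a 3-year control relapse of about 21% if follow-up runs from 0.5 to 3.5 years (the section 7.1 accrual), or about 12.5% if every patient has 3.5 years. The target is attainable but cannot be verified.

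**Exit model (all inputs below are assumptions).**

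- A share q of patients in each arm is prone to low levels: 2, 5 or 10%.
- Prone placebo patients leave in equal numbers at months 6, 12, 18, 24 and 30. Five per cent of prone active patients leave too (non-adherence).
- Prone patients have m times the relapse hazard: m = 1 (low level not prognostic) or m = 2.
- The HR is the large-sample Cox value; power is Φ(|ln HR| × √(events/4) − 1.960).

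Three policies are compared: relapse follow-up stops at exit; it continues with no vitamin D afterwards; it continues and exited placebo patients receive the full benefit of the active dose.

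True HR 0.40, follow-up 0.5 to 3.5 years; each cell is HR / power:

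| q | m | Stopped | Continued, untreated | Continued, fully treated |
|---|---|---|---|---|
| 2% | 1 | 0.400 / 0.904 | 0.400 / 0.905 | 0.402 / 0.902 |
| 2% | 2 | 0.403 / 0.903 | 0.400 / 0.909 | 0.403 / 0.903 |
| 5% | 1 | 0.400 / 0.902 | 0.400 / 0.905 | 0.405 / 0.896 |
| 5% | 2 | 0.407 / 0.901 | 0.401 / 0.915 | 0.408 / 0.901 |
| 10% | 1 | 0.400 / 0.898 | 0.400 / 0.905 | 0.409 / 0.886 |
| 10% | 2 | 0.413 / 0.897 | 0.402 / 0.924 | 0.416 / 0.897 |

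At q = 5% and m = 1, stopping costs about 0.6 placebo events (35.9 to 35.2). With 3.5 years for everyone, the largest case (q = 10%, m = 2) is HR 0.420 and power 0.878 when stopped, against 0.401 and 0.925 when continued untreated.

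**No true effect, follow-up stopped.** With m = 1 the HR stays at 1.00. With m = 2 it is 1.01, 1.01 and 1.03 for q = 2, 5 and 10% (1.01, 1.02 and 1.04 with 3.5 years for all). Removing higher-risk placebo patients flatters placebo, so the shift is against vitamin D.

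**Second model.** A separate simulation of 25(OH)D3 levels lets the hazard depend on the level itself. It assumes a placebo mean of 45 to 60 nmol/L and 70 to 100% adherence to the 25 000 IU supplement. Placebo exits ranged from 0.4 to 12.6%. At 12.6%:

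| Level after exit | HR, continued to stopped | Power, continued to stopped |
|---|---|---|
| Stays deficient | 0.407 to 0.426 | 0.868 to 0.797 |
| Rises 35 nmol/L | 0.427 to 0.426 | 0.818 to 0.797 |
| Rises 50 nmol/L | 0.434 to 0.426 | 0.800 to 0.797 |

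**Hypercalcaemia.** If 3% of active patients left, 0.27 of 14.85 active events would be lost and power would fall from 0.900 to 0.898. This is negligible.

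**The case against.** The drug-only reading has real support. The therapy entry of the synopsis ties treatment duration to the end of the study; the Table 1 column names only fall 2023 or relapse, not a laboratory value; and section 6.1.2 presents its list as safety precautions. The general follow-up rules are explicit. This stands as evidence about intent. It does not settle the matter, because a specific instruction sits against general text and section 4.3.8 itself permits early exit.

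Readers might draw four stronger conclusions that the documents do not support:

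- *A power loss of about 7 points.* The fall from 0.868 to 0.797 needs exited patients to stay deficient. Section 6.4.4 makes a level below 10 ng/ml a reportable adverse event, and section 6.2 requires care for it during and after participation. With treatment after exit, the loss is at most about 2 points in that model.
- *Exits on placebo only.* Active patients who do not take the drug could also fall below 10 ng/ml. The documents support mostly placebo, not exclusively.
- *A breach of the intention-to-treat population.* A patient censored at exit is still analysed in the randomised arm under section 7.2, and section 7.1 states a planning expectation rather than a rule. Outcome data are lost; the population is intact.
- *A fix with no power cost.* If exited placebo patients are fully supplemented, continued follow-up dilutes the contrast: at q = 5% and m = 1, power is 0.896 against 0.902 with stopping. That dilution belongs to a comparison by randomised arm whatever drug was taken, and does not justify discarding outcomes.

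The supplement for levels below 20 ng/ml should also keep exits few. The absence of a censoring rule from this file does not show that the separate analysis plan lacks one.

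**Conclusion.** The point holds as a minor one. The action is a written instruction with no definition for an individual patient, and it conflicts with the general follow-up rules. Its natural reading ends relapse follow-up on a marker that treatment changes.

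The consequence is small. If a low level is not prognostic, there is no bias and only a slight loss of events. If it doubles the hazard, assumed placebo exits of 2 to 10% move HR 0.40 to between 0.403 and 0.420. Against continued follow-up without later vitamin D, power falls by between 0.6 points (0.909 to 0.903) and 4.7 points (0.925 to 0.878). Against continued follow-up with full supplementation, stopping loses nothing material.

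A reader might infer that the rule could manufacture a benefit. It could not: with no effect the shift is to about 1.01 to 1.04, against vitamin D. In the second model stopping can give a slightly lower HR than continuing (0.426 against 0.434), but only because vitamin D works there and post-exit supplements dilute the continued comparison.

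Exit frequency, prognosis of low-level patients, control relapse rate, alpha and treatment after exit are all assumed.

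**What to change.** In section 6.1.2, replace the end of study by the end of study treatment for both triggers. In section 4.3.8, state that every randomised patient who has not withdrawn consent continues 3-monthly relapse follow-up to relapse, 3.5 years or data cut-off, and is analysed with those data. If this is already the intent, defining the term is enough. Record the date and reason of each treatment stop and any later vitamin D, and report these exits by arm in the final analysis.

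The cost is a little wording and a few extra routine visits. The statistical downside is slight dilution if exited placebo patients are then supplemented. Compared with stopping, with a non-prognostic low level and full supplementation, power falls by 0.6 points at 5% exits (0.902 to 0.896) and by 1.2 points at 10% (0.898 to 0.886). The protocol already allows open 25 000 IU supplements in either arm, so this exposure is not new in kind.
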